3 LIST OF ABBREVIATIONS

AE	adverse event
ALT	alanine aminotransferase (SGPT)
ANOVA	analysis of variance
AST	aspartate aminotransferase (SGOT)
β-HCG	beta human chorionic gonadotropin
BCRP	breast cancer resistance protein
BP	blood pressure
BUN	blood urea nitrogen
CBC	complete blood count
CHF	congestive heart failure
CI	confidence interval
CKD	chronic kidney disease
CMH	Cochran-Mantel-Haenszel
CPK	creatine phosphokinase
CRF	case report form
CRO	contract research organization
CRP	C-reactive protein
CS	clinically significant
CV	cardiovascular
CVD	cardiovascular disease
DD-CKD	dialysis dependent chronic kidney disease
dL	deciliter
DNA	deoxyribonucleic acid
DVT	deep venous thrombosis
EAC	Endpoint Adjudication Committee
ECG	electrocardiogram
EDC	electronic data capture
EOS	end of study
EOT	end of treatment
EPO	erythropoietin
ESA	erythropoiesis-stimulating agent
ESC	Executive Steering Committee
ESRD	end-stage renal disease
EU	European Union
FDA	Food and Drug Administration
g	gram
GCP	Good Clinical Practice
GFR	glomerular filtration rate
GMP	Good Manufacturing Practice
HAs	Health Authorities
HDL	high-density lipoprotein
Hb	hemoglobin
HF	Heart Failure
HIF	hypoxia-inducible factor

HIFPH	hypoxia-inducible factor prolyl-hydroxylase
HIF-PHI	hypoxia-inducible factor prolyl-hydroxylase inhibitor
IC ₅₀	50% inhibitory concentration
ICH	International Conference on Harmonisation
IDMC	Independent Data Monitoring Committee
IEC	independent ethics committee
INR	international normalized ratio
IRB	institutional review board
IV	intravenous(ly)
IWR	interactive web response
JSDT	Japanese Society for Dialysis Therapy
JSN	Japanese Society of Nephrology
KDIGO	Kidney Disease: Improving Global Outcomes
kg	kilogram
LDH	lactate dehydrogenase
LDL	low-density lipoprotein
LDO	Large Dialysis Organization
LTFU	Lost to Follow-up
LLN	lower limit of normal
MACE	major adverse cardiovascular events
mcg	micrograms
MCH	mean corpuscular (cell) hemoglobin
MCHC	mean corpuscular (cell) hemoglobin concentration
MCV	mean corpuscular (cell) volume
MedDRA	Medical Dictionary for Regulatory Activities
MI	myocardial infarction
µM	micromolar
mg	milligram
mL	milliliter
mmHG	millimeters of mercury
mRNA	messenger ribonucleic acid
ng	nanogram
ND-CKD	non-dialysis-dependent chronic kidney disease
NYHA	New York Heart Association
PD	pharmacodynamics(s)
PE	pulmonary embolism
PHD	prolyl 4-hydroxylase domain
PI	Package Insert
PK	pharmacokinetic(s)
PP	per protocol
PT	prothrombin time
PTT	partial thromboplastin time
RBC	red blood cell
RDW	red cell distribution width
ROW	rest of world
SAE	serious adverse event

SAP	Statistical Analysis Plan
SC	subcutaneous(ly)
SGOT	serum glutamic oxaloacetic transaminase (AST)
SGPT	serum glutamic pyruvic transaminase (ALT)
SmPC	summary of product characteristics
SV	Screening visit
TIBC	total iron binding capacity
TREAT	Trial to Reduce Cardiovascular Events with Aranesp Therapy
TSAT	transferrin saturation
ULN	upper limit of normal
US	United States
VEGF	vascular endothelial growth factor
WBC	white blood cell
WHO	World Health Organization

4 BACKGROUND INFORMATION

Chronic kidney disease (CKD), defined as the presence of kidney damage or a decreased level of kidney function, is a major public health problem worldwide. Globally, CKD is estimated to affect between 8% to 16% of the population ([Jha et al. 2013](#); [KDIGO 2013](#)). At the most advanced stages of CKD, end-stage renal disease (ESRD), patients require chronic dialysis or kidney transplantation to sustain life. Chronic kidney disease is not only a cause of ESRD, but is also a significant risk factor for cardiovascular disease (CVD), infection, cancer, and mortality ([Iseki and Kohagura 2007](#)).

Renal anemia often develops during the progression of CKD and is present in almost all patients with ESRD. Anemia is defined as a decrease in circulating red blood cell (RBC) mass that is usually detected by low hemoglobin (Hb) concentration. The causes of anemia in CKD include blood loss, shortened RBC lifespan, iron deficiency, erythropoietin (EPO) deficiency, and inflammation ([Nurko 2006](#)). Although many factors contribute to anemia in CKD, it occurs primarily due to an inadequate synthesis of EPO by the kidneys, leading to a deficiency in the production of RBC progenitor cells by the bone marrow. Also contributing to anemia in CKD are impaired iron homeostasis and iron loss, which often necessitate iron supplementation ([Nurko 2006](#)). Anemia in CKD patients usually occurs when the glomerular filtration rate (GFR) falls below 60 mL/min/1.73 m², and is present in >90% of the patients undergoing dialysis (CKD Stage 5) ([Goodkin et al. 2011](#)).

The main impact of anemia on organ function is reduced oxygen delivery to tissues leading to a constellation of symptoms including fatigue, shortness of breath, and exercise intolerance ([Stauffer and Fan 2014](#)). In patients with anemia related to CKD, compensatory changes occur in cardiac structure and function, including an increase in cardiac output, the development of left ventricular hypertrophy, and, eventually, the development of heart failure ([Metivier et al. 2000](#)). Risk of stroke also increases with anemia, which may be an underlying mechanism leading to stroke in CKD ([Abramson et al., 2003](#); [Iseki and Kohagura 2007](#)). Other consequences from anemia in CKD patients include impaired cognitive function, sleep disorders, and depressed immune function, which can impact the quality of life in these patients ([Iseki and Kohagura 2007](#); [NICE 2011](#)). Overall, anemia contributes to a poorer prognosis in patients with CKD ([Nurko 2006](#); [Iseki and Kohagura 2007](#)).

Erythropoiesis-stimulating agents (ESAs) administered either intravenously (IV) or subcutaneously (SC), along with oral or IV iron therapy, are currently the cornerstones for treating anemia in patients with CKD. Treatment with exogenous recombinant ESAs can raise Hb levels, relieve symptoms, and reduce the complications of anemia, including RBC transfusions which carry the risks of infection, iron overload, and impact candidacy for kidney transplantation.

Clinical practice guidelines and prescribing information for approved ESAs and guidelines provided by the United States (US) Food and Drug Administration (FDA) and the European Union (EU), differ slightly in their recommendations for treatment of renal anemia, as summarized in [Table 1](#).

Table 1 Treatment Guidelines and Prescribing Information for Renal Anemia in DD-CKD

KDIGO guidelines	Treatment should be given when Hb is between 9.0-10.0 g/dL (Kidney Disease: Improving Global Outcomes [KDIGO] 2012). ESAs should not be used to maintain Hb above 11.5 g/dL
US Aranesp alfa label	Initiate treatment when the Hgb level is less than 10 g/dL. If Hb approaches or exceeds 11.0 g/dL in adults on dialysis, the dose of ESA should be reduced or interrupted (Aranesp® US Package Insert 2017).
EU Aranesp label	Individualize dosing to achieve and maintain hemoglobin levels within the range of 100 to 120 g/L (10.0 – 12.0 g/dL). Hemoglobin levels should not exceed 120 g/L (12.0 g/dL). (Aranesp EU Label).
Japan practice guidelines	JSDT recommends that ESA treatment be initiated when Hb is below 11 g/dL following a diagnosis of renal anemia in NDD-CKD. JSN 2013 does not provide a clear recommendation or maintenance range for Hb. Both guidelines recommend that if the Hb exceeds 13 g/dL, the dose of ESA should be reduced or interrupted. In patients with CVD or complications, ESA treatment should be reduced or interrupted if the Hb exceeds 12 g/dL (Tsubakihara 2010; Japanese Society of Nephrology 2014).

Abbreviations: CVD = cardiovascular disease; DD-CKD = dialysis dependent chronic kidney disease; ESA = erythropoietin stimulating agent; EU = European Union; Hb = hemoglobin; JSDT = Japanese Society for Dialysis Therapy; JSN = Japanese Society of Nephrology; KDIGO = Kidney Disease Improving Global Outcomes; US = United States.

The majority of patients with ESRD currently receive interventional therapy in the form of iron therapy and an ESA if their Hb levels fall below 10.0 to 11.0 g/dL, dependent upon local clinical practice guidelines.

A number of large, prospective, randomized controlled trials in CKD (Stages 3 to 5) have explored the potential benefit of ESAs in patients with CKD with respect to overall mortality, cardiovascular (CV) events, and progression of CKD with higher Hb targets (≥ 13.0 g/dL) ([Besarab et al. 1998; Drüeke et al. 2006; Singh et al. 2006; Pfeffer et al. 2009a; Pfeffer et al. 2009b](#)). These trials did not demonstrate the expected beneficial effects of correcting anemia on these outcomes, but suggested an increased risk of death and CV events when targeting higher Hb levels ([Besarab et al. 1998; Drüeke et al. 2006; Singh et al. 2006; Pfeffer et al. 2009a; Pfeffer et al. 2009b](#)). Additional analyses from these trials suggest that the risk of death or CV events appears to be highest in CKD patients who fail to respond to ESAs, as indicated by lower achieved Hb levels and higher average ESA dose requirements ([Szczech et al. 2008; Solomon et al. 2010](#)). This suggests that in some subjects the ESAs themselves, and not the Hb level, may be causative of the increase in events. This is supported by studies in CKD patients on dialysis with naturally high Hb levels and no increase in CV events ([Goodkin et al. 2011](#)).

The risks identified with ESAs from these trials have led to changes in prescribing information and practice guidelines in the US, the EU, and Japan that guide clinicians toward more cautious use of ESAs and targeting lower Hb levels. In the US, the mortality and CV risks associated with ESAs are outlined in a black-box warning in the prescribing information of ESAs with a recommendation to use the lowest dose possible to avoid transfusions. While no similar major warnings exist in the EU Summary of Product Characteristics (SmPC) or on the approved labeling for ESAs in Japan, the EU SmPCs for ESAs do suggest caution with the use of these drugs, with a recommendation to keep Hb levels below 12.0 g/dL, while the Japanese practice guidelines recommend ESA treatment be reduced or interrupted if the Hb exceeds 12.0 g/dL in

patients with CVD or complications. Further, recent EU clinical practice guidelines ([Locatelli et al. 2013](#)) recommend that risk factors for stroke (including a past history of stroke) and the presence of active malignancy or a past history of malignancy should be taken into account when making decisions to use ESAs for the treatment of anemia.

The risks associated with ESAs, including an increased risk of death and CV events, highlight the need for additional therapies that might minimize or avoid these risks when compared to currently available recombinant protein-based ESAs. Therefore, the unmet medical need for the treatment of anemia in dialysis dependent CKD (DD-CKD) patients remains high, especially from a CV safety perspective. To fulfill this unmet need, the vadadustat clinical program is focused on developing an orally active therapeutic for the treatment of anemia in patients with CKD.

4.1 Hypoxia-Inducible Factor Prolyl-Hydroxylase Inhibitors

Please see the vadadustat Investigator Brochure for additional discussion and information for the following section.

Vadadustat is a synthetic, orally bioavailable, small molecule being developed as an inhibitor of hypoxia-inducible factor prolyl-hydroxylases (HIFPHs) for the treatment of anemia associated with CKD. Hypoxia-inducible factor prolyl-hydroxylase enzymes are also referred to as prolyl 4-hydroxylase domains (PHDs), of which the 2 most commonly expressed are PHD2 and PHD3. Vadadustat is a slightly more potent inhibitor of PHD3 (50% inhibitory concentration $[IC_{50}] = 0.08 \mu M$) than of PHD2 ($IC_{50} = 0.19 \mu M$). The inhibition of PHD3 and PHD2 stabilizes hypoxia-inducible factor (HIF)-2 α and HIF-1 α , which in turn stimulates the production of EPO. In vivo animal efficacy and messenger ribonucleic acid (mRNA) data indicate that vadadustat- induces the production of EPO from both renal and extra-renal sites (liver and brain), and this increase in EPO results in an increase in RBC production in the bone marrow. In clinical trials, vadadustat has been shown to facilitate iron homeostasis by decreasing hepcidin and increasing transferrin levels in healthy adult male volunteers and male and female CKD patients. This enables iron transport mechanisms that should enhance the terminal steps of erythropoiesis. Vadadustat offers the potential of flexible oral dosing that provides a more gradual and reliable means of titration than injectable hormones. Therefore, vadadustat is being developed as an alternative to the existing protein hormone ESAs.

4.2 Summary of Clinical Experience

Please see the vadadustat Investigator Brochure for additional discussion and information for the following section.

To date, the safety, tolerability, pharmacokinetic (PK), and pharmacodynamics (PD) profiles of vadadustat have been characterized in 9 completed Phase 1 studies in healthy volunteers including 1 ethno-bridging study in Caucasian & Japanese subjects, 1 completed Phase 1 study in subjects undergoing chronic hemodialysis, 3 completed Phase 2a studies in NDD-CKD subjects, 1 completed Phase 2b study in NDD-CKD subjects, and 1 completed Phase 2 study in DD-CKD subjects. The Phase 2a studies evaluated Stages 3, 4, and 5 CKD (not on dialysis) subjects in a single-dose PK study, a multi-dose, 28-day, open-label, dose escalation pilot study, and a randomized, placebo-controlled study with 5 different dose groups dosed for 42 days. The Phase 2b study evaluated Stages 3, 4, and 5 CKD (pre-dialysis) dosed for 20 weeks. The Phase 2 study evaluated DD-CKD subjects on chronic hemodialysis dosed for 16 weeks. In the studies

completed to date, a total of 548 subjects having received vadadustat, including 200 healthy volunteers and 348 subjects with CKD.

Vadadustat showed dose-dependent increases in EPO concentrations in Phase 1 and Phase 2a studies. The changes in EPO have been accompanied by an increase in reticulocytes as well as dose responsive increases in total iron binding capacity (TIBC) and decreases in hepcidin and ferritin. Overall, the safety profile for vadadustat has been acceptable and has supported further development. Vadadustat has demonstrated dose proportional PK and dose-dependent PD (changes in serum EPO and/or Hb) in Phase 1 and Phase 2 studies covering the dose range of 80 mg to 1200 mg after single administration and 500 to 900 mg after repeated daily administration. The plasma half-life of vadadustat was about 4 to 5 hours, 7 to 8 hours, and 9 to 10 hours in healthy subjects, NDD-CKD patients, and DD-CKD patients, respectively.

Vadadustat is extensively metabolized. Vadadustat and its metabolites are eliminated from the body by dual routes of elimination (both renal and fecal). The urinary excretion of vadadustat and its metabolites has been shown to be less than 60% in healthy human volunteers. In a clinical study conducted to evaluate the effect of hemodialysis on the exposures to vadadustat, hemodialysis did not have an effect on the exposures of vadadustat or its metabolites. Given its short half-life and the dual routes of elimination, vadadustat is unlikely to accumulate in patients with CKD.

A 16-week, open-label, multicenter, Phase 2 trial evaluated vadadustat in 94 subjects receiving chronic hemodialysis previously maintained on epoetin alfa. Subjects were assigned to one of three vadadustat dose cohorts: 300 mg daily, 450 mg daily, or 450 mg thrice weekly. Sixty-nine of the 94 subjects completed the study. The primary endpoint was the mean Hb change from pre-treatment average to mid-trial (Week 7-8) and end-of-trial (Week 15-16) and was analyzed using observed Hb values (no imputation for missing data). No statistically significant mean change in Hb from pre-treatment average was observed for either of the two time points for any of the three treatment groups. For all three treatment groups, group mean Hb concentrations, analyzed using observed data, remained stable at mid- and end-of-trial, with one subject with an excursion >13.0 g/dL.

Based on the Phase 1 and Phase 2 study results, vadadustat appears to be a suitable candidate for continued development as a treatment for anemia in patients with DD-CKD.

4.3 Potential Benefits and Risks

Please see the vadadustat Investigator Brochure for additional discussion and information for the following section.

Trials of injectable erythropoiesis-stimulating agents (ESAs) in patients with anemia secondary to NDD-CKD or DD-CKD have demonstrated an increased risk of cardiovascular events associated with higher Hb targets ([Besarab 1998](#); [Singh 2006](#); [Pfeffer 2009](#)). Post-hoc analyses performed by the FDA and others have shown an association between these adverse outcomes and supraphysiologic serum EPO levels and/or Hb oscillations and overshoots ([McCullough 2013](#), [Unger 2010](#)). In studies to date, oral vadadustat daily increased mean Hb with few excursions above the target range. In addition, serum EPO levels remained well below those reported with ESAs in the literature. As a result, there is the potential for the investigational drug vadadustat to provide an effective and safe therapeutic option for the treatment of renal anemia.

In addition, vadadustat may enhance iron metabolism and transport. Phase 1 and Phase 2 trials have demonstrated a consistent dose-dependent increase in TIBC and decrease in ferritin and hepcidin. Mechanistic studies have demonstrated that HIF stabilization downregulates the iron absorption regulator hepcidin, and upregulates the iron-mobilizing regulators ferroportin and transferrin (and its receptor) (Peysonnaux et al. 2007). Potential clinical benefits include enhanced erythropoiesis and decreased exogenous iron requirements.

The toxicological profile of vadadustat supports continued development in the ongoing Phase 3 clinical trials. Dose-limiting toxicity noted in the exploratory toxicology studies was due to hemoglobinuric nephropathy (rat) and emesis associated with body weight loss (dog). Dose-limiting toxicity noted in the sub-chronic and chronic toxicology studies was due to exaggerated pharmacology and the sequelae of events related to polycythemia (increased RBC mass, blood hyperviscosity and fibrin thrombi); polycythemia-related toxicity was consistent across species, monitorable and reversible. In the completed clinical studies, vadadustat has had an acceptable safety profile to support further development.

5 STUDY OBJECTIVES AND ENDPOINTS

5.1 Primary Objective

The primary objective of this study is to demonstrate the efficacy and safety of vadadustat compared with darbepoetin alfa for the maintenance treatment of anemia after correction of Hb or conversion from current ESA therapy in subjects with DD-CKD who have recently initiated dialysis treatment.

5.2 Primary Efficacy Endpoint

The primary endpoint used to assess the efficacy objective will be the mean change in Hb between Baseline (mean pretreatment Hb) and the primary evaluation period (mean Hb from Weeks 24 to 36).

5.3 Secondary Efficacy Endpoints

The key secondary efficacy endpoints include the following:

- Mean change in Hb value between Baseline (mean pretreatment Hb) and the secondary evaluation period (Weeks 40 to 52).
- Proportion of subjects with Hb values within the target range during the primary evaluation period (Weeks 24 to 36).
- Proportion of subjects with Hb values within the target range during the secondary evaluation period (Weeks 40-52).

Other secondary efficacy endpoints include:

- Proportion of time with Hb values within the target range during the primary evaluation period (Weeks 24-36).
- Proportion of time with Hb values within the target range during the secondary evaluation period (Weeks 40-52).
- Proportion of subjects with Hb increase of >1.0 g/dL from Baseline.
- Time to achieve Hb increase of >1.0 g/dL from Baseline.

- Mean change in Hb between Baseline (mean pretreatment Hb) and the primary evaluation period (mean Hb from Weeks 24-36) stratified by pre-Baseline ESA exposure.
- Proportion of subjects receiving RBC transfusion(s) from Baseline to Week 52.
- Proportion of subjects receiving IV iron therapy from Baseline to Week 52.
- Mean monthly dose of IV elemental iron administered from Baseline to Week 52 in subjects who have received IV iron.
- ESA rescue.
- Dose adjustments from Baseline to Week 52.

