8.4 Treatment of Subjects

8.4.1 Treatment Group Assignments

Subjects will be randomized in a 1:1 ratio via the IWR system to either:

- Vadadustat (starting dose of 2 tablets once daily [300 mg/day]).
- Darbepoetin alfa IV/SC (starting dose based on the current PI for investigational sites in the US and the SmPC for all other investigational sites [non-US] for adult patients with CKD on dialysis).
 - For subjects already on darbepoetin alfa, the initial dosing regimen in the study should be based on the prior dosing regimen.

Target enrollment for each treatment group is approximately 150 subjects.

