8.4.3 Blinding

This will be an open-label study. Treatment assignment will be done through the IWR system and the Investigator, Sponsor, and CRO study teams will not be aware of which treatment will be assigned next. Treatments will be administered in an open-label fashion.; The Sponsor and CRO study teams will be blinded to ‘by treatment’ aggregated analyses except for the unblinded statistician. Because Hb values are objective and will be measured via a central laboratory for all efficacy endpoints, efficacy assessments are not considered to be subject to bias with an open-label design. In addition, the study will involve blinded adjudication of MACE, the use of an IDMC, and an identical schedule of visits, procedures, and assessments for both treatment groups in order to reduce the potential for bias. However, certain personnel directly involved in medical oversight of the study, regulatory reporting of safety information, and on-site monitoring activities may become unblinded to the treatment assignments of individual subjects during the course of the study. In addition, in order to reduce subjectivity of dose adjustment, adjustments to doses for vadadustat and darbepoetin alfa will be based on Hb concentration and Dose Adjustment Algorithms.

The EAC will remain blinded throughout the full course of the study.

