8.4.6 Iron Supplementation

Investigators will prescribe iron supplementation (IV, oral, or intradialytic) during the study to maintain ferritin ≥ 100 ng/mL or TSAT $\geq 20\%$.

Important: Because of the potential for iron to reduce the bioavailability of vadadustat, the study medication is not to be administered concurrently with an oral iron supplement (including multivitamins containing iron), iron containing phosphate binders, or any other medications containing iron. The subject should be instructed to take these medications at least 2 hours before or 2 hours after the dose of vadadustat.

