11.6.2 Secondary Efficacy Analyses

Secondary efficacy endpoints analyses will be performed using the randomized and full analysis populations and the assigned treatment as described in [Section 11.2, Study Analysis Populations](#). Analysis for the key secondary efficacy endpoints will be repeated using the PP population with the actual treatment received.

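### The IV iron dose endpoint averages only over subjects who received IV iron, so it compares groups selected after randomization and can understate or reverse an iron saving

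*Protocol*

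**What the plan says.** Section 5.3 and the Efficacy Endpoints part of the synopsis give the same definition, so the restriction is not a slip in one place: "Mean monthly dose of IV elemental iron administered from Baseline to Week 52 in subjects who have received IV iron". A separate endpoint in both lists is the "Proportion of subjects receiving IV iron therapy from Baseline to Week 52". No endpoint in the current protocol averages the IV iron dose over all subjects.

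Four other places bear on the point:

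- Section 4.3 on the expected effect: "Potential clinical benefits include enhanced erythropoiesis and decreased exogenous iron requirements".
- Section 8.4.6 on who decides: "Investigators will prescribe iron supplementation (IV, oral, or intradialytic) during the study". The decision is tied to ferritin and TSAT.
- Section 8.4.3: "Treatments will be administered in an open-label fashion".
- Section 11.6.2 on populations: "Secondary efficacy endpoints analyses will be performed using the randomized and full analysis populations and the assigned treatment".

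**The concern.** The denominator is fixed by something that happens after randomization and that treatment may change. If vadadustat removes the need for IV iron in subjects whose need is small, those subjects leave the vadadustat average. Their counterparts stay in the darbepoetin alfa average. The vadadustat recipients who remain then have greater need on average, and the contrast no longer has the protection of randomization.

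Selection could also run the other way. Sections 4.2 and 4.3 report that vadadustat lowers ferritin and raises TIBC, and ferritin and TSAT are what prompt iron prescribing. The arm is known when the choice is made, and IV is only one of three routes.

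The restriction also sits badly with Section 11.6.2. That section assigns secondary endpoints to populations defined by assigned treatment, but the endpoint's wording removes every subject without IV iron. Such a subject has an observed dose of 0 mg, not a missing value.

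At stake is the only endpoint that measures iron dose, on a benefit the protocol itself puts forward. As defined, it does not estimate IV iron use under each assigned treatment.

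**Working it through.** **Figure to reproduce.** The protocol gives no rate, dose, variance, effect or power for IV iron, so there is nothing to reproduce. The only trial figure used is the arm size from Section 8.4.1: "Target enrollment for each treatment group is approximately 150 subjects". Every iron rate and dose below is an assumption.

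**1. Identity.** In each arm,

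mean over all = (proportion receiving) × (mean among recipients).

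Hence

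ratio of recipients' means = (ratio of all-subject means) ÷ (ratio of proportions receiving).

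The recipients' mean moves the wrong way whenever the proportion receiving falls by a larger fraction than the all-subject mean does.

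**2. Worked example, 150 per arm.** Control: 120 recipients at 150 mg/month, total 120 × 150 = 18,000. Vadadustat: the 45 lowest users, at 50 mg/month, need none and nobody else changes, total 18,000 − 45 × 50 = 15,750.

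- All subjects: 18,000/150 = 120 against 15,750/150 = 105, a saving of 15 mg/month.
- Recipients only: 18,000/120 = 150 against 15,750/75 = 210, an apparent excess of 60 mg/month.

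The same arithmetic under other assumptions, with a control recipients' mean of 150 throughout:

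| Control recipients | Stop on vadadustat | All-subject mean, control vs vadadustat | Recipients' mean, control vs vadadustat |
|---|---|---|---|
| 120 of 150 | 15 at 50 mg | 120 vs 115 | 150 vs 164 |
| 90 of 150 | 30 at 50 mg | 90 vs 80 | 150 vs 200 |
| 135 of 150 | 30 at 100 mg | 135 vs 115 | 150 vs 164 |

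A separate simulated case fits the identity. With 70% of controls and 49% of vadadustat subjects receiving IV iron, and all-subject means of 77.2 and 70.0 mg/month, the recipients' means are 77.2/0.70 = 110.3 and 70.0/0.49 = 142.9. A 9% saving shows as a 30% excess.

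**3. Less selective effects.** In a latent-need model (2,000,000 draws), need was log-normal with median 100 mg/month and IV iron was given above a threshold of 25, 50 or 100. Ratios are vadadustat to control.

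| Effect on need | Log SD of need | All-subject ratio | Recipients-only ratio |
|---|---|---|---|
| 20% cut for everyone | 0.5 to 1.5 | 0.60–0.80 | 0.80–0.92 |
| 20 mg cut for everyone | 0.5 | 0.71–0.82 | 0.86–0.99 |
| 20 mg cut for everyone | 1.0 to 1.5 | 0.87–0.95 | 1.02–1.10 |

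A proportional effect is mostly understated. A fixed reduction is understated when need varies little and reversed when it varies more. Constant shifts of a normal latent need (four settings) gave falls of 25–36% over all subjects against 15–22% among recipients.

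**4. What one trial would show.** 5,000 simulated trials per row, 150 per arm. In the control arm 50% are high users (mean 210 mg/month), 30% are low users (mean 50) and 20% use none; within-group log SD is 0.4. A share of the low users stops on vadadustat.

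| Low users who stop | All-subject difference | Recipients-only difference | Recipients-only estimate favours darbepoetin alfa | Recipients-only 95% CI wholly above 0 |
|---|---|---|---|---|
| none | −0.1 | −0.2 | 48% | 2.5% |
| 33% | −5.0 | +14.2 | 84% | 18% |
| 67% | −10.3 | +33.4 | 99% | 65% |
| all | −15.1 | +59.8 | 100% | 99% |

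With no effect, both analyses behave properly. The problem arises only when treatment changes who receives IV iron.

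**The case against.** The strongest reply is that the missing half is already listed. The proportion receiving IV iron is an endpoint in its own right, and multiplying it by the recipients' mean recovers the all-subject mean. In the 70% against 49% case a reader of both results would see the drop in users. Section 11.6 also promises only descriptive summaries by treatment group for other secondary endpoints, and the protocol states no test or margin for this one. That limits the harm, and it stands. It does not remove the point. If the proportion falls while the recipients' mean rises, the reader has two opposing signals, no listed endpoint that settles them, and no interval for the product.

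A second reply is that reversal needs an effect concentrated in low users or a wide spread of need, that the figures are assumed, and that Section 4.3 speaks only of a potential benefit. This also stands: several of the models give understatement with the right sign.

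Third, the illustrations all work against vadadustat, so none shows a false claim of iron sparing. That follows from how they were set up. Swap the arms in the first example and vadadustat uses more IV iron (120 against 105 mg/month over all subjects), yet its recipients' mean looks lower (150 against 210).

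Finally, an all-subject IV mean scores a subject on oral iron alone as 0 mg, so it is not total iron use. That is true, but the current endpoint does not measure total iron use either, and the all-subject version is at least a randomized comparison of IV dose.

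**Conclusion.** The concern holds. The protocol's own definition conditions on receipt of IV iron, which follows randomization, is decided with the arm known, and may be changed by the drug. The resulting mean can understate an iron saving or reverse its sign. Under the assumptions tried, results ran from attenuation (for example 0.85 among recipients against 0.76 over all subjects) to full reversal (+60 mg/month shown for a true saving of 15). Which would occur here cannot be said, because the protocol gives no iron-use rates or doses.

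The weight is moderate. This is an other secondary endpoint, the companion proportion is pre-specified, and no primary, key secondary or MACE conclusion depends on it. The statistical analysis plan may add an all-subject analysis, but the restriction is written into the protocol's endpoint definition and would remain there.

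**What to change.** In Section 5.3 and the synopsis, delete the phrase that limits the endpoint to recipients. Define it as the mean monthly IV elemental iron dose over all randomized subjects: each subject's total IV dose up to Week 52 divided by that subject's time in study up to Week 52, with 0 for those who received none. Keep the proportion receiving IV iron as it is. Show the recipients' mean beside it as description, without a treatment comparison.

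The cost is one phrase in two places, and no new data are needed. The price is a skewed distribution with many zeros, for which a bootstrap or rank-based interval is suitable. Precision is also modest: in the simulated trials above, the all-subject 95% CI lay wholly below 0 in only 6%, 12% and 21% of trials for true savings of about 5, 10 and 15 mg/month. The estimate would nevertheless address the right question and carry the right sign on average.
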